4.4 Early Withdrawal of Subjects

4.4.1 When and How to Withdraw Subjects

Subjects may be withdrawn if they experience any serious adverse reactions to the radioligand or during the participation in the study.

4.4.2 Data Collection and Follow-up for Withdrawn Subjects

No data collection will occur after withdrawal in subjects who drop out of the study. If data was collected prior to withdrawal, such data will be analyzed if possible.

5 Study Drug

5.1 Description

^{18}F -MK-6240 is a novel tau radioligand recently developed by Merck & Co., Inc [26]. ^{18}F -MK-6240 shows favorable binding properties in both human brain homogenates and rhesus monkey brain PET studies [27]. Pharmacological studies have shown that the unlabeled compound MK-6240 is not expected to have any significant binding to other targets that would confound measurement of tau aggregation. Early human PET studies have shown that ^{18}F -MK-6240 binding is elevated in AD patients, and that resulting radiation exposure is within the range of other ^{18}F radioligands.

Florbetaben is indicated for PET imaging of the brain to estimate β -amyloid neuritic plaque density in adult patients with cognitive impairment who are being evaluated for AD and other causes of cognitive decline. A negative Florbetaben scan indicates sparse to no amyloid neuritic plaques and is inconsistent with a neuropathological diagnosis of AD at the time of image acquisition; a negative scan result reduces the likelihood that a patient's cognitive impairment is

CONFIDENTIAL

This material is the property of Columbia University Medical Center. Do not disclose or use except as authorized in writing by the study sponsor.

due to AD. A positive Florbetaben scan indicates moderate to frequent amyloid neuritic plaques; neuropathological examination has shown this amount of amyloid neuritic plaque is present in patients with AD but may also be present in patients with other types of neurologic conditions as well as older people with normal cognition. Florbetaben is an adjunct to other diagnostic evaluations.

5.2 Preparation and Administration of Study Drug

Participant preparation includes intravenous catheterization followed by administration of 8.1 mCi as a slow single intravenous bolus (6 sec/mL) in a total volume of up to 10 mL of ¹⁸F-Florbetaben for A β PET imaging and 5 mCi of ¹⁸F-MK-6240 for tau PET.

¹⁸F-MK-6240 will be formulated in clear solution of up to 10% (v/v) ethanol, and 0.5% sodium ascorbate in saline (0.9% sodium chloride) for IV bolus administration.

¹⁸F-Florbetaben is supplied in a 30 mL glass vial containing up to 30 mL of a clear solution at a strength of 50 to 5000 MBq/mL (1.4 to 135 mCi/mL) ¹⁸F-florbetaben at end of synthesis. Each vial contains multiple doses and is enclosed in a shielded container to minimize external radiation exposure.

5.3 Packaging

N/A since ¹⁸F-MK-6240 will be packaged and provided by Cerveau and ¹⁸F-Florbetaben will be packaged and provided by Life Molecular Imaging.

5.4 Receiving, Storage, Dispensing and Return

5.4.1 Receipt of Drug Supplies

Upon receipt of the of the study treatment supplies, an inventory must be performed and a drug receipt log filled out and signed by the person accepting the shipment. It is important that the designated study staff counts and verifies that the shipment contains all the items noted in the shipment inventory. Any damaged or unusable study drug in a given shipment (active drug or comparator) will be documented in the study files. The investigator must notify study sponsor of any damaged or unusable study treatments that were supplied to the investigator's site.

5.4.2 Storage

Store ¹⁸F-Florbetaben and ¹⁸F-MK-6240 at room temperature 25°C (77°F); excursions permitted to 2°C to 42°C (36°F to 108°F). The product does not contain a preservative. Store within the original container or equivalent radiation shielding. Radiotracer must not be diluted.

This preparation is approved for use by persons under license by the Nuclear Regulatory Commission or the relevant regulatory authority of an Agreement State.

CONFIDENTIAL

This material is the property of Columbia University Medical Center. Do not disclose or use except as authorized in writing by the study sponsor.

5.4.3 Dispensing of Study Drug

Slow bolus (6 sec/mL) IV injection of 5 mCi ^{18}F -MK-6240 and 8.1 mCi ^{18}F -Florbetaben on the same day as delivery to the Columbia University Medical Center PET Department.

For ^{18}F -MK-6240, the carrier mass dose will be limited to no more than 20 μg per injection. For ^{18}F -Florbetaben, the carrier mass dose will be limited to no more than 30 μg per injection.

5.4.4 Return or Destruction of Study Drug

At the completion of the study, there will be a final reconciliation of drug shipped, drug consumed, and drug remaining. This reconciliation will be logged on the drug reconciliation form, signed and dated. Any discrepancies noted will be investigated, resolved, and documented prior to return or destruction of unused study drug. Drug destroyed on site will be documented in the study files.

6 Study Procedures

6.1 Tau PET

The ^{18}F -MK-6240 PET scans are acquired over a period between 30 to 60 minutes in 6 to 12 x 5 minute frames on the same scanner, beginning 60 to 80 minutes after injection.

Transmission scans are done prior to the emission scan. An accompanying structural CT scan (in-plane resolution=0.58×0.58 mm, slice thickness=3mm, FOV=29.6×29.6 cm, number of slice=75) is also acquired.

6.2 Amyloid PET

The ^{18}F -Florbetaben PET scans are acquired over a period of 20 minutes in 4 × 5 minute frames on an MCT PET/CT scanner (Siemens) in dynamic, 3D imaging mode beginning 90 minutes after injection.

Transmission scans are done prior to the emission scan. An accompanying structural CT scan (in-plane resolution=0.58×0.58 mm, slice thickness=3mm, FOV=29.6×29.6 cm, number of slice=75) is also acquired.

The second PET visit will occur within 24 months of the first. There is no particular order that the participants must receive the study drugs. If eligible, the MRI scan will be collected up to 18 months prior to the first PET visit, or up to 18 months after the second PET visit.

6.3 Questionnaires

Participants may be asked to complete any number of outstanding questionnaires during the PET scan uptake periods. The questionnaires are self-administered and are part of the planned data collection for the main Offspring study.

CONFIDENTIAL

This material is the property of Columbia University Medical Center. Do not disclose or use except as authorized in writing by the study sponsor.

7 Statistical Plan

7.1 Sample Size Determination

The sample size of 150 subjects was selected to allow sufficient power ($\geq 80\%$) of a two-sided significance test with $\alpha = 0.05$ to detect meaningful effects associated with the primary hypotheses. We used the G*Power[28] to perform the following power analyses.

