w/v	Weight by volume
v/v	Volume by volume
NOAEL	No-observed-adverse-effect-level
³ H	Tritium
K _d	Equilibrium dissociation constant
FTD	Frontotemporal dementia
ICH	International Conference on Harmonization
MNI	Molecular NeuroImaging
AE	Adverse events
VOI	Volumes of interest
BP _{ND}	Binding potential
HV	Healthy volunteer
DVR	Distribution volume ratio
SoT	Standard of Truth
BSS	Bielschowsky silver staining
CERAD	Consortium to Establish a Registry for Alzheimer's Disease
DLB	Dementia with Lewy bodies
ECG	Electrocardiogram
SAE	Serious adverse event
ECI	Extracorporeal irradiation
CT	Computed tomography
ED	Effective dose
Sv	Sievert
Gy	Gray

CONFIDENTIAL

This material is the property of Columbia University Medical Center. Do not disclose or use except as authorized in writing by the study sponsor.

FOV	Field of view
MPRAGE	Magnetization Prepared Rapid Acquisition Gradient Echo
ROI	Region of interest
FS	FreeSurfer
CRF	Case report form
UP	Unexpected problem
HIPAA	Health Insurance Portability and Accountability Act
PHI	Protected health information

CONFIDENTIAL

This material is the property of Columbia University Medical Center. Do not disclose or use except as authorized in writing by the study sponsor.

Study Summary

Title	Alzheimer's PET Imaging in Racially/Ethnically Diverse Adults
Short Title	Alzheimer's PET Imaging in Racially/Ethnically Diverse Adults
Protocol Number	AAAR8986
Phase	I
Methodology	
This is a single center PET Study.
 
Racially/ethnically diverse subjects with or without a positive family history of Alzheimer's disease (AD) will have one PET scan with ¹⁸F-MK-6240 over a 30 to 60-minute scanning period, and one PET scan with ¹⁸F-Florbetaben over a 20-minute scanning period.

Study Duration	5 years
Study Center(s)	Kreitchman PET Center
Objectives	The purpose of this study is to examine the extent to which tau deposition is related to cognitive function, to determine whether tau deposition varies across racial/ethnic groups, to determine the extent to which cerebrovascular disease (CVD) is associated with tau pathology, and to determine if any of those associations depend on amyloid status.
Number of Subjects	150

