A β and tau PET scans will be obtained on a representative subset of 150 offspring (with and without positive family history of AD) between the age of 35 and 85. We will prioritize individuals who have already undergone or will undergo structural MRI as part of the Offspring Study. We will obtain both PET scans within 24 months of each other. Therefore, about 33 individuals per year will be recruited and scanned for contemporaneous A β and tau PET and MRI scanning. MRI scans will be completed up to 18 months prior to the first PET scan, or up to 18 months after the last PET scan. Since MRI scanning has already commenced in the overall study, we will re-acquire MRI scans (with other funds) in instances when the initial scan falls outside of the 18-month window. A subset of PET eligible subjects may be ineligible for MRI scans due to contraindications. To allow us to continuously meet recruitment goals, we will still obtain PET scans on these individuals and use an adjusted statistical method during data analysis. Specially, PET data collected without MRI data will be quantified as parametric standard uptake value ratio (SUVR) images using atlas-based regions of interest (ROIs) rather than subject-specific, MRI-based ROIs. The Montreal Neurological Institute (MNI) brain atlas will undergo a non-linear spatial transform to PET space. An inferior cerebellar gray matter ROI from the MNI template will be used as reference region. Alzheimer's disease specific ROIs from the MNI template will be used to derive mean SUVRs. A covariate for analysis method (atlas-based ROIs vs subject-specific, MRI-based ROIs) will be included in all statistical analyses.

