7.2 Statistical Methods

Regional SUVR for ^{18}F -MK-6240 will be calculated to investigate associations with measures of memory, olfactory function, and cerebrovascular disease, and amyloid positivity for ^{18}F -Florbetaben will be calculated to investigate the potential moderation of amyloid on the associations with tau.

Before any specific statistical modelling techniques are applied, we will examine all variables for illegitimate values, outliers, and other inconsistencies. Distributions of demographic and other clinically important variables will be examined and summarized by means, standard deviations, minima, and maxima for continuous measures and proportions for categorical measures. Similar descriptive analyses will be conducted on all outcome variables of interest. We will make every effort to obtain all data to reduce or eliminate missing data issues. Tests will be two-sided and performed at a significance level of $\alpha=0.05$. After descriptive examination of the variables of interest, a series of unadjusted or partially adjusted planned analyses will be conducted to address the specific hypotheses, followed by fully adjusted models, follow-up analyses, and exploratory analyses. In all regression analyses, steps will be taken to avoid issues related to multicollinearity of the predictors. If necessary, data reduction techniques (e.g., screening out variables that are highly correlated) will be applied to the predictors prior to fitting the regression models.

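### Does the claim of at least 80% power at 150 participants overstate what the study can say about amyloid dependence?

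*Combined protocol and SAP*

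**What the plan says.** Section 7.1 says "The sample size of 150 subjects was selected to allow sufficient power", at least 80% with two-sided alpha 0.05, "to detect meaningful effects associated with the primary hypotheses". It then says "We used the G*Power[28] to perform the following power analyses", but in the text available for this review section 7.2 follows directly. No test, effect size, number of covariates or group split is shown, and the primary hypotheses are not listed.

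Amyloid enters in three places. The objectives in the Study Summary end with the aim "to determine if any of those associations depend on amyloid status". Section 3.2 names amyloid positivity, beside regional tau SUVR, as the primary outcome measure. Section 7.2 says amyloid positivity will be used "to investigate the potential moderation of amyloid on the associations with tau". The expected share of amyloid-positive participants is not given.

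Section 4.3 says that some participants will be unable to have an MRI; for them, "we will still obtain PET scans on these individuals and use an adjusted statistical method during data analysis". They count toward the 150, although the cerebrovascular question in section 2 uses MRI markers.

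**The concern.** A reader who sees amyloid dependence among the objectives, and one blanket power statement in section 7.1, may apply that statement to the amyloid question. A test of whether an association differs between two groups is limited by the smaller group, here probably the amyloid-positive participants. The only rate in the document for cognitively normal people is the healthy-volunteer row of Table 4: 26 of 188, or 13.8%. Applied to 150, that is about 21 people.

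At stake is how a null result is read. A non-significant interaction might be reported as showing that the association does not depend on amyloid, with section 7.1 cited in support, when the test had little chance of detecting a moderate difference. The cerebrovascular hypothesis also has somewhat fewer than 150 participants.

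**Working it through.** **The plan's own figure.** The 80% cannot be reproduced, because section 7.1 gives no effect size or test. It can only be turned round to ask what 150 participants can detect.

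**1. Single association.** Fisher z, two-sided 0.05, 80% power:

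atanh(r) = (1.960 + 0.842) / sqrt(n − 3)

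- n = 150: 2.802 / sqrt(147) = 0.231, so r = 0.227.
- As a one-degree-of-freedom regression term (noncentral F), this corresponds to f² = 0.053.
- Three equal groups (number and sizes assumed): f = 0.256.

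The claim is therefore attainable for small-to-moderate main associations.

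**2. Cerebrovascular question.** Sections 3.3 and 4.1 say only that the number without MRI is small. Assuming 15 or 30 are missing, the detectable r is 0.239 (n = 135) or 0.253 (n = 120), against 0.227. The difference is minor.

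**3. Amyloid moderation as a difference of two correlations.** With n1 positives and 150 − n1 negatives:

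SE = sqrt(1/(n1 − 3) + 1/(147 − n1)); power = Φ(q/SE − 1.960) + Φ(−q/SE − 1.960), where q is the difference in atanh(r).

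Assume r = 0.3 against 0, so q = 0.3095. The value n1 = 21 comes from the healthy-volunteer row of Table 4; the others are assumed.

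| Positives | SE | q/SE | Power |
|---|---|---|---|
| 15 (10%) | 0.3015 | 1.027 | 18% |
| 21 (14%) | 0.2520 | 1.228 | 23% |
| 30 (20%) | 0.2135 | 1.450 | 31% |
| 45 (30%) | 0.1833 | 1.688 | 39% |
| 75 (50%) | 0.1667 | 1.857 | 46% |

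Simulating the regression interaction under the same assumptions gave 17%, 24%, 38% and 45% at 10%, 13.8%, 30% and 50% positive, which agrees.

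**4. How far the result depends on the inputs.**

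- *Effect size.* With r = 0.5 against 0 (q = 0.549), power is 59% at 21 positives and 85% at 45. At 21 positives, 80% power needs q = 2.802 × 0.2520 = 0.706, or r = 0.61 against 0.
- *Share of positives.* The same Table 4 has 28 of 50 positive in mild cognitive impairment (56%) and 139 of 176 in Alzheimer's disease (79%). Section 4.1 admits people with mild cognitive impairment and mild Alzheimer's disease, in unstated proportions. Section 3.1 defines positivity by clustering SUVR values with an any-region rule, whereas Table 4 reports readers' interpretations of images, so the rate may not carry over.
- *Spread of tau.* Section 7.2 plans regression, where moderation is a difference in slopes: SE = sqrt(1/((n1 − 1)s²) + 1/(149 − n1)), in residual SD per tau SD, with s the ratio of tau SD in positives to that in negatives. If s = 2, a slope difference of 0.3 has power 47%, 56%, 63% and 68% at 15, 21, 30 and 45 positives; a difference of 0.4 has 71%, 80%, 87% and 90%. If s = 1, a difference of 0.3 has 19%, 24%, 31% and 39%. A wider spread is plausible: section 1.4 reports SUVR up to 4.0 in Alzheimer's disease against about 0.5 to 1.5 in healthy volunteers, though in only six subjects.

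**The case for a change.** The strongest case for a change is that the direction does not depend on the share of positives. For correlations of 0.3 against 0 with equal tau spread, even an even split gives only 46%, and 0.4 against 0.1 gives 49%. Amyloid dependence is a stated objective, section 7.1 does not exclude it, and a few sentences would prevent misreading. It is no answer that a conventional medium interaction (f² = 0.15) would have over 99% power: with equal spread and about 14% positive, that means roughly r = 0.75 against 0.

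The arithmetic stands, and so does the remark that the visible section 7.1 shows no effect size, test or expected share of positives. The inference that the section overstates its power does not. The section limits itself to unquantified effects under unlisted primary hypotheses. Naming amyloid positivity within the primary outcome measure does not make the interaction a primary hypothesis, and section 7.2 treats moderation only as a possibility to be investigated. The age argument, that healthy volunteers in Table 4 were older than this cohort, is also weak: the median of 72 years belongs to all 461 subjects of Study C, including 182 with Alzheimer's disease, and the volunteers' own ages are not given.

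The missing calculation may be lost text. Table 6 is cited in section 4.3 and is likewise absent from the text available here.

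**Conclusion.** No change is needed. The power statement can be neither confirmed nor refuted as written. It is attainable for single associations of about r = 0.23 or larger, and slightly larger for the cerebrovascular question.

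For amyloid moderation, 18% to 46% is right if the correlations are 0.3 and 0, tau spread is equal, all 150 have usable data and 10% to 50% are amyloid-positive. None of those inputs is set by the plan. With tau SD doubled in positives, a slope difference of 0.4 reaches 80% at 21 positives.

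What remains is missing detail. Stating detectable effects would change no enrolment, model or estimate. Nothing in the plan says a non-significant interaction will be read as no dependence. An analyst reporting moderation in a cohort of 150 would be expected to give the interaction estimate with its confidence interval and the number of positives, and those show directly how much the data can say.

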7.2 Statistical Methods

Regional SUVR for ^{18}F -MK-6240 will be calculated to investigate associations with measures of memory, olfactory function, and cerebrovascular disease, and amyloid positivity for ^{18}F -Florbetaben will be calculated to investigate the potential moderation of amyloid on the associations with tau.

Before any specific statistical modelling techniques are applied, we will examine all variables for illegitimate values, outliers, and other inconsistencies. Distributions of demographic and other clinically important variables will be examined and summarized by means, standard deviations, minima, and maxima for continuous measures and proportions for categorical measures. Similar descriptive analyses will be conducted on all outcome variables of interest. We will make every effort to obtain all data to reduce or eliminate missing data issues. Tests will be two-sided and performed at a significance level of $\alpha=0.05$. After descriptive examination of the variables of interest, a series of unadjusted or partially adjusted planned analyses will be conducted to address the specific hypotheses, followed by fully adjusted models, follow-up analyses, and exploratory analyses. In all regression analyses, steps will be taken to avoid issues related to multicollinearity of the predictors. If necessary, data reduction techniques (e.g., screening out variables that are highly correlated) will be applied to the predictors prior to fitting the regression models.

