Evaluation of radiation dosimetry has been performed following administration of [¹⁸F]MK-6240 in three healthy humans (two females and one male). The average (\pm SD) value of ED was 29.4 ± 0.6 μ Sv/MBq, which is in the typical range for ¹⁸F-radiolabelled ligands. The radioactivity widely distributed to various body organs with organ absorbed doses largest for the gallbladder (202 μ Gy/MBq), small intestine (116 μ Gy/MBq), upper large intestine (128 μ Gy/MBq) and urinary bladder (128 μ Gy/MBq). Based on this, the administration of one 185 MBq (5 mCi) of [¹⁸F]MK-6240 for PET scanning is anticipated to result in a total human ED of about 5.4 mSv.

The overall safety profile of Florbetaben is based on data from 978 administrations of Florbetaben to 872 subjects and 12 subjects who received vehicle only. No serious adverse reactions related to Florbetaben administration have been reported. The most frequently observed adverse drug reactions in subjects receiving Florbetaben were injection site reactions consisting of erythema, irritation and pain. All adverse reactions were mild to moderate in severity and of short duration.

The effective dose resulting from a 300 MBq (8.1 mCi) administration of Florbetaben in adult subjects is 5.8 mSv. The use of a CT scan to calculate attenuation correction for reconstruction of Florbetaben images (as done in PET/CT imaging) will add radiation exposure. Diagnostic head CT scans using helical scanners administer an average of 2.2 ± 1.3 mSv effective dose (CRCPD Publication E-07-2, 2007). A low-dose head CT attenuation scan administers a 0.04 mSv effective dose. The actual radiation dose is operator and scanner dependent.

Thus, the total combined radiation exposure from MK-6240 and Florbetaben administration and subsequent scan on a PET/CT scanner is estimated to be $5.4\text{mSv} + 5.8\text{mSv} + 2 * 0.04\text{mSv} = 11.28\text{ mSv}$.

2 Study Objectives

The study employs tau PET imaging in a well-characterized multi-racial/ethnic cohort to examine the extent to which tau pathology is associated with cognition, differences in tau pathology across racial/ethnic groups, and the relationship between MRI markers of small-vessel cerebrovascular disease and tau pathology. The study also investigates amyloid-dependent tau spreading.

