4.1 Inclusion Criteria

We will limit our recruitment into this study to people who are between 35 and 85 years old at the time of enrollment, with or without confirmed WHICAP parent history of AD, and who are currently enrolled in the ongoing Offspring Study. Recruitment will focus on those individuals who did or will undergo structural MRI scanning as part of this Offspring study within 18 months of PET study participation. A small number of subjects who enroll in the PET study may have contraindications to MRI scanning, for which we have an adjusted method of image analysis in place as described in Section 4.3 below.

The participants must meet the following:

1. Age 35-85 years
2. Have either mild cognitive impairment or mild clinical Alzheimer's disease; or have no problem with memory or thinking
3. Able to participate in all scheduled evaluations and to complete all required tests and procedures
4. Must be considered likely to comply with the study protocol and to have a high probability of completing the study

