4.3 Subject Recruitment and Screening

Adult children from the WHICAP study are currently being recruited into the Offspring Study. The parents are a selected subset of participants in WHICAP who are active (seen at the most recent assessment wave) or inactive (deceased, moved, too ill to participate) and seen at baseline and at least one follow-up. We recruit from families in which parents with and without AD are demographically matched. Table 6 shows the number of WHICAP families from which we are recruiting offspring, given the current prevalence of AD among WHICAP participants and the expected conversion rate over 5 years among active participants. Our preliminary data suggest that on average, we will have access to two to three offspring who live in the greater NYC area.

We plan to assess 600 offspring per year for all five years of the Offspring Study, and obtain medical, neuropsychological, and functional data from an in-person visit. We are recruiting approximately 33% of the offspring to participate in brain MRI. These 1,000 (n=200 per year)

offspring will be representative of the cohort at large with respect to parent diagnosis, race/ethnicity, and sex. All offspring will be screened for eligibility for structural brain MRI. Table 6 shows our expected MRI recruitment based on our experience in the WHICAP study, our pilot interview data of offspring, and conservative estimates of eligibility and willingness

to be scanned. Only one offspring per family will be recruited for the MRI. If there are more than one offspring who are eligible for MRI within a family, we select the oldest. Of eligible families, we expect that 75% of offspring will be eligible after screening for MRI contraindications, and of those, 60% will be willing to participate (willingness rate was 79% in our survey), and thus we will have 1,079 eligible and willing MRI participants.

CONFIDENTIAL

This material is the property of Columbia University Medical Center. Do not disclose or use except as authorized in writing by the study sponsor.

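### Does Section 7.2 need to name one deciding model, with age in it, before crude and adjusted tests are both run at 0.05?

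*Combined protocol and SAP*

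**What the plan says.** Section 7.2 sets out a sequence. After descriptive work, "a series of unadjusted or partially adjusted planned analyses will be conducted to address the specific hypotheses, followed by fully adjusted models", and then follow-up and exploratory analyses. One level covers them all: "Tests will be two-sided and performed at a significance level of" 0.05. Highly correlated predictors may be screened out before a model is fitted.

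Section 4.3 names one covariate: "A covariate for analysis method (atlas-based ROIs vs subject-specific, MRI-based ROIs) will be included in all statistical analyses". Section 4.1 limits recruitment to "people who are between 35 and 85 years old at the time of enrollment"; in the available text age is an eligibility limit and is not named as a model term. On sampling, Section 4.3 says of the MRI subset that these "offspring will be representative of the cohort at large with respect to parent diagnosis, race/ethnicity, and sex", and for families with several candidates, "If there are more than one offspring who are eligible for MRI within a family, we select the oldest".

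Section 7.1 gives 150 participants for at least 80% power on the primary hypotheses and says "We used the G*Power[28] to perform the following power analyses". No power analysis follows in the text supplied, and the section numbering runs from 7.3 straight to 14.

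**The concern.** Each hypothesis appears to be tested at least twice at 5%, with no stated order of precedence. If a crude model and an adjusted model disagree, either could be reported as the answer after both have been seen.

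Age makes this more than a formality. Tau burden, memory and "the relationship between MRI markers of small-vessel cerebrovascular disease and tau pathology" are all quantities that may move with age, and the age range spans 50 years. A crude association could appear with none present at a given age. A racial/ethnic difference in tau could likewise reflect a difference in mean age. The correlation screening in Section 7.2 protects no variable, so on a literal reading age could be dropped even from the fully adjusted model.

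**Working it through.** **The plan's own figure.** Section 7.1 gives N = 150, power of at least 80% and two-sided 0.05, but the available text has no effect size, so 150 cannot be reproduced. Solving backwards for a correlation by Fisher's z: r = tanh[(1.960 + 0.842)/√(150 − 3)] = tanh(0.231) = 0.227. Ten covariates move this only to 0.235, so adjustment costs little through degrees of freedom.

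**Error of a test that omits age.** Assume no association given age, and age correlations a and b with the two variables. The crude correlation is then a·b. With m = atanh(a·b)·√147, the rejection rate is Φ(m − 1.96) + Φ(−m − 1.96).

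| a, b (assumed) | a·b | m | Crude test rejects |
|---|---|---|---|
| 0, 0 | 0 | 0 | 5.0% |
| 0.3, 0.1 | 0.03 | 0.364 | 6.5% |
| 0.2, 0.2 | 0.04 | 0.485 | 7.7% |
| 0.3, 0.3 | 0.09 | 1.094 | 19.4% |
| 0.4, 0.4 | 0.16 | 1.957 | 49.9% |

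The crude rate reaches 10% at a·b = 0.054, or 0.23 each.

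**Both tests together.** In simulation (40,000 datasets of 150), equal correlations of 0.2, 0.3 and 0.4 give at least one significant result in about 9.6%, 21.8% and 52.5% of datasets. The two verdicts differ in 6.2%, 19.2% and 49.9%. The age-adjusted test alone stays between 5.0% and 5.2%. At 0.3 and 0.1, either test is significant in about 8%.

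**No confounding.** If the covariates explain a share R² of the outcome and are unrelated to the predictor, the two test statistics correlate √(1 − R²). The chance that at least one is significant is 5.0% at R² = 0, 5.7% at 0.02, 6.5% at 0.1, 7.6% at 0.3 and 8.3% at 0.5. The 9.75% for two independent tests (1 − 0.95²) overstates this setting, because both models use the same data.

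**Group contrast.** Assume two groups of 50, an 8-year gap in mean age and an age–tau correlation of 0.4. Uniform ages from 35 to 85 have SD 50/√12 = 14.4. The spurious standardized difference is 0.4 × 8/14.4 = 0.22, and a t test on 98 degrees of freedom rejects 19.5% of the time. With a 3-year gap and correlation 0.2 the rate is 5.5%. An age SD of 10 with the correlation held at 0.4 gives 35%, but that steepens the age slope. Holding the slope and residual variance fixed, the slope is 0.4/14.43 = 0.0277 outcome SD per year, and the correlation at SD 10 becomes 0.277/√(0.84 + 0.277²) = 0.29. The difference is then 0.29 × 8/10 = 0.23 and the rate about 21%. The 8-year case is therefore about 20% at either SD.

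**Reading the passages together.** Section 4.3 requires the image-analysis covariate in every analysis. Read literally, a strictly unadjusted test is ruled out wherever that covariate varies, and the first tier is at least partially adjusted. Whether that tier includes age is not stated. If it does, the figures of 19% and above do not arise.

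**The case for a change.** The case for acting is that all the alternative readings leave something open. If the phrase about addressing the hypotheses makes the first tier decisive, the deciding test may lack age. If the fully adjusted model decides, nothing says so. Including age in the full model does not settle precedence once both results are known. The remedy would be a few words of SAP text, and age is already recorded.

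The literal points stand: the available text has no ranking of models and no covariate list, and the word unadjusted sits awkwardly beside Section 4.3. The arithmetic also stands under its assumptions.

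The weight placed on them does not. The largest error rates need a deciding test without age, together with equal and fairly strong age correlations with both variables. The documents give neither. The sampling rules add little: confounding comes from age variation within the sample, so matching on other traits neither causes nor cures it, and taking the oldest sibling does not show imbalance between groups. The hypotheses to which a covariate list would attach are themselves missing from the supplied text, along with the announced power analyses and Table 6, so a covariate not being named is weak evidence that it was not planned.

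Nor is the remedy wholly free. At a fixed slope and residual variance, a predictor–age correlation of 0.3, 0.4 or 0.6 (assumed) would lower 79.8% power to 76%, 73% or 61%, although the loss cancels if age explains as much of the outcome as of the predictor.

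**Conclusion.** No change is called for. Crude models followed by adjusted ones are ordinary practice in a single-center observational imaging study. Section 7.2 plans both tiers, and showing both makes any disagreement visible to a reader. An analyst of tau, memory and vascular markers over a 50-year age range would include age in the full model and would not let a collinearity screen remove it. What is left is detail that analysts fill sensibly and that the missing part of Section 7.1 may already supply.

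The possible size runs from almost nothing (crude error of 5% to 8% when age is weakly related to either variable) to large (about 19% to 50% at correlations of 0.3 to 0.4 with both). The upper end depends on assumed correlations and on a deciding test that omits age. This is an ambiguity of wording, and no error in the plan has been shown.
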